7.7.1 Dose adjustment rules for Tier 1, C1D1 (D0) and interval study visits

Tier 1 - C1D1 (D0)

Overview of study visit interval:

All subjects begin treatment on C1D1 (D0) at DL1 of vactosertib (50mg BID). All subjects return one week (7 days \pm 2) after C1D1 (D0) and the vactosertib dose is adjusted according to the dose adjustment rules defined in Section 7.7.1 Table 3. The study visit interval is weekly (7 days \pm 2) any time the dose adjustment rule dictates dose escalation or a dose hold. If the dose adjustment rule dictates maintaining the current dose, then the visit interval is extended to approximately every 2 weeks. After at least two, consecutive 'Maintain' dose-adjustment decisions at the same dose level, then the next visit is extended to no later than Day 1 of the next cycle of vactosertib (approximately every 4 weeks).

Once Tier 1 has enrolled 3 patients, enrollment will be held until each patient has completed at least the first cycle of therapy before enrollment is re-opened.

Study Visit Interval Based Upon Dose Adjustment Decision:

All subjects begin treatment on C1D1 (D0) at DL1 of vactosertib (50mg BID for Tier 1). All subjects return one week (7 days \pm 2) after C1D1 (D0) and the vactosertib dose is adjusted according to the dose adjustment rules defined in Section 7.7.1 Table 3. The study visit interval is weekly (7 days \pm 2) any time the dose adjustment rule dictates dose escalation or a dose hold. If the dose adjustment rule dictates maintaining the current dose, then the visit interval is extended to approximately 2 weeks. After at least two, consecutive Maintain dose-adjustment decisions at the same dose level, then the next visit is extended to no later than Day 1 of the next cycle of vactosertib (approximately every 4 weeks).

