7.7.2 Dosing Delays/Dose Modifications for vactosertib

Clinical Parameter	Escalate to Next Dose Level	Maintain Current Dose Level	Hold Dose	Restart After Dose Hold
Erythropoietic Response	Inadequate	Adequate		
Hemoglobin (HGB) absolute value, change in HGB from baseline*, and Erythrocyte transfusion	HGB ≤10 g/dL AND ≤2 g/dL increase from baseline HGB OR any Erythrocyte transfusion	HGB >10 g/dL OR >2g/dL increase from baseline HGB AND No Erythrocyte transfusion	HGB >12 g/dL	HGB<12 g/dL
Current Toxicity (CTCAE v5)	≤Grade 2	≤Grade 2 OR >Grade 2 not requiring change in treatment	>Grade 2 Requiring Change in Treatment	<Grade 2 and Requiring No New Change in Treatment
Dose hold Toxicity during Cycle	Dose Hold Not Required During Cycle	Dose Hold Not Required During Cycle		
Current Dose Dose Levels: (DL0) 50 mg daily; (DL1) 50 mg bid; (DL2) 100 mg bid; (DL3) 150 mg bid; (DL4) 200 mg bid.	< Highest Dose Level	≤ Highest Dose Level		Most Recent Dose >(DL0)
Dosing schedule, 5 days on, 2 days off				
Rule	All True	All True	Any True	All True
Next Study Visit [†]	7±2 days	1 st Maintain [§] 14±3 days 2 nd or greater Maintain D1 of next cycle	7±2 days	7±2 days

Table 3: Intrapatient Dose Adjustment Rules.

The parameters shown are used to adjust the vactosertib dose on a continuing basis. The dose is escalated to the next level if ALL criteria for escalation are met. The decision to Hold vactosertib is made if ANY hold criteria is met at any point during the cycle. Otherwise the dose level is maintained. The criteria to Escalate, Maintain or Hold a dose are non-overlapping. Dose decrements by one level will follow any HOLD. * Baseline HGB is defined as the median HGB in the 4 weeks prior to D1 of protocol treatment. † Subject will maintain a diary of adverse events between study visits. [§]Visits are weekly if there is a dose change (Escalate, Hold or Restart). Visits are bi-weekly if the decision is to Maintain the current dose. Visits are extended to every 4 weeks (D1 of each new cycle) after the second or greater, consecutive Maintain decision.

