8.1.1 Discontinuation of Study Intervention

8.1.1. Tier 1 Stopping Rule:

The primary objective of Tier 1 is to assess the feasibility of protocol therapy in subjects with advanced MPNs as measured by the incidence of dose limiting toxicity (DLT, see *Definition of Dose Limiting Toxicity* section). Toxicities are assessed by CTCAEv5 criteria. Up to a total of 12 patients will be accrued to Tier 1. Tier 1 will be stopped for safety considerations under the following conditions:

- Any patient has grade 5 (lethal) DLT occurring within the first 12 weeks of starting vactosertib; or
- More than two patients experience a dose-limiting toxicity (DLT) at any dose, within the first 12 weeks on study.

Trial accrual will be suspended and a DSMB convened if either of these *Tier 1 Stopping Rule* criterion is triggered. If more than two patients have a DLT at the same dose level, then further accrual to that dose level and higher dose levels will be suspended. Pending review with DSMB, the study may be re-opened with amendment reflecting changes to the permitted dose levels. A planned stop to Tier 1 accrual will occur after 12 subjects have received at least one dose of vactosertib. At this time, the DSMB will be convened if fewer than 1 of the first 12 patients experience clinical benefit.

Protocol therapy will be considered safe if the *Tier 1 Stopping Rule* is not triggered. The following table provides the marginal probability of declaring the intervention unsafe for different rates of severe toxicity (as defined by *Tier 2 Stopping Rule*). This *Tier 1 Stopping Rule* protects against an unexpectedly high rate of severe toxicity.

Tier 1	True Rate of Severe Toxicity				
	5%	10%	15%	20%	30%
Probability of Declaring Unsafe	12%	35%	56%	73%	91%

If the Tier 1 safety boundaries are not crossed, this treatment strategy will be considered safe for expansion to Tier 2. Feasibility and toxicity will continue to be monitored in the Tier 2 portion of the study. A total of 37 patients will be accrued (Tier 1 + Tier 2) and the Tier 2 rule stopping rule applies to all subjects (up to 37) enrolled.

8.1.2. Tier 2 Stopping Rule:

- Any patient has grade 5 (lethal) DLT occurring within the first 12 weeks of starting vactosertib; or

- More than five patients experience a dose-limiting toxicity (DLT) at any dose, within the first 12 weeks on study.

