12.5 Interim Analysis

Reports of toxicity and efficacy will be submitted for DSMB review at the following time points:

- completion of Tier1;
- completion of Tier2;
- any time one of the stopping rules is met.

Unscheduled Interim Analysis will be performed if more than three patients have a DLT at the same dose level or if more than five patients in both tiers, at any dose level, have a DLT. In the former situation, further accrual to that dose level and higher dose levels will be suspended. In the latter situation, further accrual to the study will be halted. Reports of toxicity and efficacy will be submitted for DSMB review in that instance for review and guidance as to whether the dose level can be re-opened or accrual to the study can proceed and if the study should be amended to permanently close the problematic dose levels or closed altogether.

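### The dose-level suspension in 8.1.1 and 12.5 is not carried into the escalation and restart rules that set each patient's dose

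*Combined protocol and SAP*

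**What the plan says.** **Suspension.** Section 8.1.1 (Tier 1 Stopping Rule): "If more than two patients have a DLT at the same dose level, then further accrual to that dose level and higher dose levels" is to be suspended. It continues: "Pending review with DSMB, the study may be re-opened with amendment reflecting changes to the permitted dose levels". Section 12.5: "Unscheduled Interim Analysis will be performed if more than three patients have a DLT at the same dose level", and "In the former situation, further accrual to that dose level and higher dose levels will be suspended". The DSMB then gives "guidance as to whether the dose level can be re-opened or accrual to the study can proceed".

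**Overall limits.** Tier 1 accrual is suspended if "More than two patients experience a dose-limiting toxicity (DLT) at any dose, within the first 12 weeks on study", or on any grade 5 DLT in that window. Section 8.1.2 sets the Tier 2 limit at more than five patients within 12 weeks, counted over all 37. It has no per-level clause.

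**Dosing.** Section 7.7.1 starts every Tier 1 patient at DL1 (50 mg twice daily). Under Table 3 (section 7.7.2), "The dose is escalated to the next level if ALL criteria for escalation are met". Those criteria are the patient's own hemoglobin, transfusions, toxicity and hold status, plus a current dose below the highest level. The listed levels end at DL4, which 6.3.3.1 calls the maximum. On dose, restart requires only that the last level was above DL0; 6.3.3.4 then drops the patient one level. Section 6.3.6.4 applies the same scheme to Tier 2.

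**The concern.** The suspension is written in terms of accrual to a level. In Tier 1 nobody is accrued to DL2, DL3 or DL4; patients climb there. The suspension therefore works only if it stops escalation and restart, and the rules used at each visit do not say that it does. The references to permitted levels and to a level being re-opened suggest that closing the level to everyone was intended.

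A safe and tolerable dose is a primary objective, and DLT and possible MTD identification are primary endpoints in both tiers. In Tier 2 the per-level rule is the only stated cross-patient safeguard aimed at one toxic level before the overall limit is reached. A site that follows Table 3 to the letter could dose a patient at a level the protocol has closed.

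**Working it through.** **1. The rules side by side.** Take Tier 2 starting below DL3, with four patients having a DLT at DL3, no grade 5 DLT and no more than five DLT patients overall.

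- 12.5 suspends DL3 and DL4. The overall limit is not met, so enrolment continues.
- A DL2 patient with inadequate hemoglobin response, toxicity of grade 2 or less and no hold that cycle meets every escalation criterion and moves to DL3.
- A patient held at DL4 restarts one level down, at DL3.
- Nothing in Table 3 or 6.3.3 blocks either step. The conflict lasts until the DSMB acts.

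In Tier 1 the overall rule normally stops new accrual at the same time, so the gap there mainly concerns patients already on treatment.

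**2. The plan's own figures.** The plan gives no operating characteristics for the per-level rule. The nearest is the Tier 1 table for the overall rule (12, 35, 56, 73, 91% at true rates 5, 10, 15, 20, 30%). The exact binomial for more than two of 12 gives 2.0, 11.1, 26.4, 44.2, 74.7%. Two or more of 12 gives 11.8, 34.1, 55.6, 72.5, 91.5%, which fits the printed row within about one point. That is a separate matter; the written counts are used below.

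**3. Chance that a level closes in Tier 2 while the study stays open.** Inputs from the plan: 12 then 25 patients, Tier 1 passed with at most two DLT patients, closure at four at one level, study limit at six. Assumed: true DLT rate p, and spread w of DLTs over DL1 to DL4 (even; half at one level; 80% at one level; the remainder shared equally).

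Let T be the DLT count if all 37 are enrolled. A level closes before the sixth DLT if T = 4 with all four at one level, or if T is at least 5 with at least four of the first five at one level:

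P = P(pass, T=4) × a4 + P(pass, T≥5) × a5

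- a4 = Σw⁴ = .0156 / .0648 / .4097 (even / half / 80%)
- a5 = Σ[w⁵ + 5w⁴(1−w)] = .0625 / .1975 / .7376

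| p | P(pass, T=4) | P(pass, T≥5) | even | half | 80% |
|---|---|---|---|---|---|
| 5% | .0691 | .0281 | 0.3% | 1.0% | 4.9% |
| 10% | .1856 | .2232 | 1.7% | 5.6% | 24% |
| 15% | .1425 | .4227 | 2.9% | 9.3% | 37% |
| 20% | .0609 | .4534 | 2.9% | 9.4% | 36% |

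Example, p = 10% and 80% at one level: .1856 × .4097 + .2232 × .7376 = .0760 + .1646 = .2407.

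The grade 5 rule and the 12-week windows are ignored.

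**4. How many patients.** By enrolment order, the median closing patient is number 31–32 at p = 5%, 29–30 at 10%, 27–28 at 15% and 24–25 at 20%. That leaves 37 − 32 = 5 to 37 − 24 = 13 still to enrol. At the projected 2 per month (section 12.2), 24 / 52.18 = 0.46 new patients per week. If Tier 2 starts below the closed level and all climb weekly, at most 0.46 × 2 = 0.9 would reach it in a two-week review and 0.46 × 4 = 1.8 in a four-week review (lengths assumed). Patients at lower levels who later meet the escalation criteria would add to this.

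**5. The two counts in Tier 1.** They lead to different actions only with exactly three DLT patients, all at one level, and at least one DLT after week 12. P(X=3 of 12) = .0852 at p = 10% and .2362 at 20%. P(all at one level) = Σw³ = .0625 / .1389 / .5129. P(at least one late) = 1 − .75³ = .578 if 25% of DLTs are late, or 1 − .90³ = .271 if 10% are (shares assumed).

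| Late share | p = 10% (even / half / 80%) | p = 20% (even / half / 80%) |
|---|---|---|
| 25% | 0.3 / 0.7 / 2.5% | 0.9 / 1.9 / 7.0% |
| 10% | 0.1 / 0.3 / 1.2% | 0.4 / 0.9 / 3.3% |

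If the per-level sentence shares the 12-week window, the result is zero.

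**The case against.** The best defence is that Table 3 governs the individual patient while 8.1 and 12.5 hold the cross-patient stops, and that a specific safety suspension would ordinarily override routine titration. On that view the level is already barred and only a cross-reference is missing. This is a plausible account of the intent, but no text states which rule takes precedence, and 6.3.3.1 names DL4 as the maximum without qualification.

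Other protections exist: weekly visits after escalation, holds with a step down for toxicity above grade 2 that requires a treatment change, the grade 5 rule, investigator withdrawal and DSMB reports. They limit harm, but none closes a level.

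A reader might also infer that the two counts are a serious contradiction. With 12 patients exposed at one level and a 20% DLT rate, three or more occur with probability 44.2% and four or more with 20.5%. The documents do not support giving that contrast weight in Tier 1, where three DLT patients within 12 weeks already suspend all accrual. Both rules can be obeyed there by acting at three, and in Tier 2 only the count in 12.5 is stated. What stands is that 12.5 carries no tier label and neither per-level sentence states a window.

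**Conclusion.** The main point holds: 8.1.1 and 12.5 close a level, and the rules that set each patient's dose do not carry the closure out. In Tier 2 the chance of reaching that state is about 0.3 to 4.9% at a 5% DLT rate, 1.7 to 24% at 10%, 2.9 to 37% at 15% and 2.9 to 36% at 20%. These ranges rest on assumed rates and, above all, on how concentrated the DLTs are; the high end is the case of one clearly toxic level, which is what the rule is for.

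It would be tempting to conclude that many patients would be treated at a toxic dose. The documents do not support that: closure tends to come late, accrual is slow, and DSMB review is triggered at once. The differing counts are secondary. Overall the point lies between a minor clarification and a change that should be made, and the low cost favours making it.

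**What to change.** - Add to Table 3 and 6.3.3 that no patient may escalate or restart into a suspended level pending DSMB review, and that a restart which would land there goes to the highest open level below it.
- Define the highest dose level in Table 3, and the maximum in 6.3.3.1, as the highest level still open.
- Label the per-level count by tier in 8.1.1 and 12.5: more than two in Tier 1 and more than three across both tiers, or one common count. The sponsor and DSMB choose.
- State whether the 12-week window applies to it.

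The cost is amendment wording, with no extra patients or procedures. The downside is that some patients with an inadequate response stay at a lower dose during the review.

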6.3.6. Tier 2 Treatment Plan

The study will proceed to Tier 2 as long as vactosertib is deemed safe and tolerable according to predefined criteria (see *Criteria for Decision to Proceed to Tier 2* and *Statistical Considerations and Justification of Proposed Sample Size* sections). The Tier 2 arm will enroll additional patients to reach a statistically predetermined cohort size that can preliminarily assess efficacy of vactosertib, or lack thereof, with sufficient power and statistical significance (see *Statistical Considerations and Justification of Proposed Sample Size* section).

6.3.6.1. Screening, enrollment and registration for Tier 2 will be performed as described for Tier 1.

6.3.6.2. Treatment phase of Tier 2 including clinical follow-up visits and rules for dose adjustment and/or removal from study will proceed as for Tier 1 with the possible exception of starting dose level.

6.3.6.3. Starting Dose for Tier 2:
The starting dose on Tier 2 will be identified as follows:

- The lowest dose level of vactosertib for which no DLT was observed in Tier 1 AND The lowest dose level for which at least one of the 12 subjects enrolled on Tier 1 met *Criteria for Clinical Benefit*.
- Or, if a single dose level does not fulfil both Criterion 1 and Criterion 2, the starting dose level for Tier 2 will lowest dose from Tier 1 for which no DLT was identified.

6.3.6.4. Each subject will follow *Intrapatient Dose Adjustment Rules* (Table 3). The same schema for dose escalation and monitoring for toxicity outlined in the description of the Tier 1 patients will be followed.

6.3.6.5. Subjects enrolled on Tier 2 will have bone marrow exam at the end of Cycle 4 (approximately Week 16 ± 7 days).

6.3.6.6. End of Tier 2 testing and procedures will be performed as per Tier 1 End of cycle 4 testing and procedures with the exception that it will be performed after completion of the 6th cycle of vactosertib. An End of Tier bone marrow exam is not required for subjects enrolled on Tier 2 since a scheduled exam is performed at the completion of Cycle 4.

6.3.6.7. After the planned 6 cycles of study treatment, subjects meeting the criteria for ongoing treatment (see Section [6.3.7 Ongoing Treatment for Patients Demonstrating Clinical Benefit](#)) will have the option to continue receiving vactosertib until disease progression or unacceptable toxicity.

6.3.7. Ongoing Treatment for Patients Demonstrating Clinical Benefit:

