12.1 Study Design/Endpoints

12.1.1. Optimal Two-Stage Design, and Criteria to Proceed to Tier 2:

A Simon Two-stage Optimum Design was used to minimize the number of subjects exposed to vactosertib if it is found to be an unsuitable agent for the treatment of anemic patients with Ph-neg MPNs. Further development of vactosertib would be warranted if $\geq 20\%$ of subjects met *Criteria for Clinical Benefit* ([section 10.1](#)) without dose-limiting toxicity (see *Definition of Dose Limiting Toxicity* section). The study will be terminated early if fewer than 1 subject treated in the first tier (up to 12 subjects) meet these criteria. Using these criteria, there is less than a 10% chance of inappropriately accepting (α , type 1 error) vactosertib if it is not truly useful. Conversely, there is less than a 10% chance of inappropriately rejecting (β , type 2 error) vactosertib if it is actually a useful drug for anemic patients with Ph-neg MPNs.

Table 4: Optimal Two Stage Design

Response Probability Indicating Unacceptably Low vactosertib Activity	0.05
Response Probability Indicating Substantial vactosertib Activity	0.20
Probability of Accepting Poor Drug	0.1
Probability of Rejecting Good Drug	0.1
Number of Tier 1 Subjects	12
Number of Tier 1 Responders to Advance to Tier 2	≥ 1
Maximal Number of Subjects	37
Number of Tier 2 Responders to Advance Development	≥ 4

The Simon Two-stage Optimum Design is expected to minimize the number of subjects exposed to vactosertib if it is found to be an unsuitable agent for the treatment of anemic patients with Ph-neg MPNs (see *Criteria for Decision to Proceed to Tier 2* section). If 1 or more subjects meets the *Composite Response & Toxicity Endpoint* ([Table 5](#)) then the study will proceed to Tier 2 and another 25 subjects will be enrolled. After completion of Tier 2, if four or more subjects meet the *Composite Response & Toxicity Endpoint* then vactosertib

will have shown preliminary efficacy and feasibility to justify further evaluation as an agent to treat anemic patients with Ph-Neg MPNs.

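### The Tier 1 futility rule differs between sections 8.1.1 and 12.1.1 in action, endpoint and timing, and the stated type I error holds only if the stop at 0 of 12 is binding

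*Combined protocol and SAP*

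**What the plan says.** Section 12.1.1 gives a Simon optimal two-stage design with 12 subjects, then 25 more, and success at 4 or more responders of 37. On futility it is categorical: "The study will be terminated early if fewer than 1 subject treated in the first tier" meets clinical benefit without dose-limiting toxicity. It then makes Tier 2 conditional on at least one subject meeting the Table 5 composite, which requires clinical benefit lasting at least 8 weeks and no dose-limiting toxicity. The error claims follow: "Using these criteria, there is less than a 10% chance of inappropriately accepting" a poor drug, and "Conversely, there is less than a 10% chance of inappropriately rejecting" a useful one.

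Section 8.1.1 plans a halt to accrual once 12 subjects have had at least one dose, and continues: "At this time, the DSMB will be convened if fewer than 1 of the first 12 patients experience clinical benefit". It does not say that the study ends, it does not mention the composite, and the check is tied to the accrual halt.

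Other sections touch the same decision:
- Section 10.1 says the clinical benefit criteria are used for deciding on Tier 2, without the Table 5 conditions.
- Section 12.5 puts the DSMB report at completion of Tier 1. Section 15 puts the Tier 1 data report there too, and proceeds with one or more responders.
- Section 12.6.2 assesses response in subjects who have had at least 4 cycles.
- Section 6.3.6 says "The study will proceed to Tier 2 as long as vactosertib is deemed safe and tolerable" and refers to the predefined criteria and the statistical section.

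**The concern.** Sections 8.1.1 and 12.1.1 differ on three things that must be fixed before the data are seen: what happens at 0 of 12, which event is counted, and when the count is made.

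- **Action.** The type I error in 12.1.1 is computed for a trial that stops at 0 of 12. If convening the DSMB can lead to continuation, that figure no longer describes the trial. The saving in exposed patients, which is the stated reason for the design, can also be lost.
- **Event.** A subject with brief benefit, or with benefit and a dose-limiting toxicity, passes the check in 8.1.1 but is not a responder under Table 5.
- **Time.** A subject who has just started cannot have had 8 weeks of benefit. A check at the accrual halt counts such subjects in the denominator before they can respond.

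At 0 of 12, different parties could each cite a different section for what should follow.

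**Working it through.** **Inputs.** From Table 4: "Response Probability Indicating Unacceptably Low vactosertib Activity 0.05", "Response Probability Indicating Substantial vactosertib Activity 0.20", "Number of Tier 1 Subjects 12", a maximum of 37 subjects, at least 1 responder to advance, and at least 4 of 37 for success. From section 12.2: 2 entries per month. From section 7.7.1: an enrolment hold after 3 patients until each has completed one cycle. All probabilities are exact binomial.

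**1. The plan's own figures, with a binding stop at 0 of 12.**
P(success) = sum over x ≥ 1 of P(X₁ = x | 12, p) × P(X₂ ≥ 4 − x | 25, p).

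At p = 0.05:

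| Tier 1 responders | Probability | Needed in the next 25 | Probability | Product |
|---|---|---|---|---|
| 1 | 0.3413 | ≥ 3 | 0.1271 | 0.0434 |
| 2 | 0.0988 | ≥ 2 | 0.3576 | 0.0353 |
| 3 | 0.0173 | ≥ 1 | 0.7226 | 0.0125 |
| ≥ 4 | 0.0022 | none | 1 | 0.0022 |

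The sum is 0.0935 (products rounded). At p = 0.20 the same formula gives 0.9024. Both stated error limits are met, and a grid search confirms that this is the Simon optimum for these inputs.

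Early stop under the null: 0.95^12 = 0.540. Expected sample size under the null: 12 + 25 × (1 − 0.540) = 23.5.

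**2. Stop not binding.** Let q be the chance that the trial continues after 0 of 12.
- At p = 0.05 the added probability of success is q × 0.5404 × P(X ≥ 4 | 25, 0.05) = q × 0.5404 × 0.0341 = 0.0184q.
- Type I error = 0.0935 + 0.0184q.
- It equals 0.10 at q = (0.10 − 0.09347) / 0.01842 = 0.354.
- At q = 1 it is P(X ≥ 4 | 37, 0.05) = 0.1119. Power is then 0.9550, and all 37 subjects are treated under the null.

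**3. Check made when the twelfth subject starts.** Assume one entry every half month, which is 30.4375 / 2 / 7 = 2.17 weeks. Weeks on study, from the first subject to the twelfth, are then 23.9, 21.7, 19.6, 17.4, 15.2, 13.0, 10.9, 8.7, 6.5, 4.3, 2.2 and 0. Four subjects have at least 16 weeks and eight have at least 8 weeks. Treating the hold as one month between the third and fourth entries changes neither count.

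With m subjects evaluable, P(no responder | p = 0.20) = 0.8^m. If the study were terminated on 0 of m, power would be the sum over x ≥ 1 of P(x | m, 0.20) × P(X ≥ 4 − x | 37 − m, 0.20).

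| Evaluable subjects | P(no responder), true rate 20% | Power if terminated on 0 of m |
|---|---|---|
| 12 (design) | 6.9% | 90.2% |
| 8 (≥ 8 weeks on study) | 16.8% | 81.1% |
| 4 (≥ 16 weeks on study) | 41.0% | 57.9% |

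The row for 8 is the favourable limit on the composite, because it needs benefit to begin at once and last. The row for 4 uses the 4-cycle requirement of section 12.6.2.

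**The case against.** The best defence is that the sections can be read together. Section 8.1.1 does not say the trial continues after 0 of 12; convening the DSMB is compatible with ending the study under 12.1.1. Its provision for re-opening by amendment belongs to the toxicity triggers. Sections 12.5, 12.6.2 and 15 give a workable time, so the wording in 8.1.1 may only be loosely placed.

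Much of this stands, and it rules out several stronger readings:

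- **That 6.3.6 is a third rule, opening Tier 2 on safety alone.** Its sentence names only safety and tolerability, but it refers to the statistical criteria, which require a responder. The protocol summary requires efficacy and safety endpoints. The sentence in 8.1.1 about uncrossed boundaries is a safety conclusion, not a full rule to proceed.
- **That type I error simply exceeds 10%.** It does so only if continuation after 0 of 12 is likelier than about 35%, and power rises at the same time.
- **That 41% is the chance of a false alarm.** It is the upper end of a range. If plain clinical benefit is counted at any visit, as 8.1.1 allows, more subjects could contribute and the figure would be lower. That count would not be the event on which the design rests.
- **That a good drug would be stopped early.** Under 8.1.1 it would be flagged. No section applies the 12.1.1 termination at that look.

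What the defence does not remove is the difference in wording on action, endpoint and time. The protocol also gives the DSMB no criterion for the case of 0 of 12.

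**Conclusion.** The inconsistency is real and should be corrected. The design in 12.1.1 is sound as computed: 9.35% type I error and 90.2% power with a binding stop. Section 8.1.1 does not state that stop. If it is not binding, type I error lies between 9.35% and 11.2%, an excess of at most 1.2 percentage points over the stated limit (11.2 − 10), and expected exposure under the null rises from 23.5 towards 37 subjects. The exposure is the larger consequence.

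A check at the twelfth subject's start would raise the chance of seeing no responder to a 20%-active drug from 6.9% to about 17% to 41%. This rests on even entry at 2 per month and on counting the composite. Power would fall, to about 81% or 58%, only if termination were applied at that look, which the documents do not direct.

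**What to change.** State one futility rule in the same words in sections 6.3.6, 8.1.1, 10.1, 12.1.1 and 15:

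*Once all 12 Tier 1 subjects have completed week 16 or left the study, the trial stops for futility if 0 of 12 meet the Table 5 composite. Subjects who left without meeting the composite count as non-responders.*

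Section 12.6.2 needs a matching line, because it now limits response assessment to subjects with at least 4 cycles.

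If the sponsor prefers DSMB discretion, 12.1.1 should declare the stop non-binding and give type I error as up to 11.2%.

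The change concerns futility only. The separate safety stopping rule, with its DSMB review and possible re-opening by amendment, stays as it is.

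The cost is wording. The review time matches the completion of Tier 1 already set in 12.5 and 15, and the halt to accrual after 12 subjects is already planned. The non-binding option costs a slightly less favourable stated error rate.

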Protocol therapy will be considered safe if the *Tier 2 Stopping Rule* is not triggered. The following table provides the marginal probability of declaring the intervention unsafe for different rates of severe toxicity (as defined by *Tier 2 Stopping Rule*). The *Tier 2 Stopping Rule* protects against an unexpectedly high rate of severe toxicity.

Tier 2	True Rate of Severe Toxicity				
	5%	10%	15%	20%	30%
Probability of Declaring Unsafe	3.1%	31%	67%	89%	99%

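### An untriggered stopping rule is reported as therapy being safe, with no estimate or upper limit for the DLT rate required anywhere in the plan

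*Combined protocol and SAP*

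**What the plan says.** Section 8.1.1 sets two triggers for Tier 1. One is a death: "Any patient has grade 5 (lethal) DLT occurring within the first 12 weeks of starting vactosertib". The other is a count: "More than two patients experience a dose-limiting toxicity (DLT) at any dose, within the first 12 weeks on study". On size it says: "Up to a total of 12 patients will be accrued to Tier 1".

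If neither trigger fires, the section concludes: "Protocol therapy will be considered safe if the *Tier 1 Stopping Rule* is not triggered". After its probability table it adds a qualified version: "If the Tier 1 safety boundaries are not crossed, this treatment strategy will be considered safe for expansion to Tier 2". It then promises continued surveillance: "Feasibility and toxicity will continue to be monitored in the Tier 2 portion of the study".

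Section 8.1.2 keeps the grade 5 trigger, sets the count limit at more than five patients with a DLT, and concludes: "Protocol therapy will be considered safe if the *Tier 2 Stopping Rule* is not triggered". Section 8.1.1 applies that rule to all subjects, up to 37.

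The protocol summary and section 1.2.1 make safety and tolerability a primary objective. Section 12.4.1 refers only to Table 4 and section 12.1, which set out a response design. Section 12.6.1 makes all treated patients evaluable for toxicity and leaves the rest to be completed with the Biostatistics Office. Sections 8.1 and 12 contain no acceptable DLT rate, no estimate of the rate and no confidence limit.

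**The concern.** A stopping rule is built to halt a trial when toxicity is clearly excessive. When it stays silent, toxicity has not been shown to be excessive. With 12 or 37 patients, that is much weaker than showing that toxicity is low. The sentences in 8.1.1 and 8.1.2 turn the weak statement into a positive one, and no analysis section supplies the missing inference.

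The wording would need correcting even if both probability tables were exact. Those tables describe how the rule behaves before data are collected. They do not say which DLT rates an observed count has ruled out. A reader told that therapy is considered safe after 2 DLTs in 12 patients (16.7%) or 5 in 37 (13.5%) would take more from the result than the data hold.

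**Working it through.** **Inputs.** Tier 1 has n = 12 and passes with 2 or fewer DLTs (8.1.1). The Tier 2 rule has n = 37 across both tiers and passes with 5 or fewer (8.1.1, 8.1.2). True rates are those heading the printed tables. Patients are treated as independent, with a common DLT rate and all evaluable. The grade 5 trigger is left out at first.

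**Step 1: reproduce the plan's own figures.** The probability of declaring unsafe is P(X ≥ r) with X ~ Binomial(n, p).

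| True rate | 5% | 10% | 15% | 20% | 30% |
|---|---|---|---|---|---|
| Tier 1, printed | 12% | 35% | 56% | 73% | 91% |
| Written rule, ≥3 of 12 | 2.0% | 11.1% | 26.4% | 44.2% | 74.7% |
| One lower, ≥2 of 12 | 11.8% | 34.1% | 55.7% | 72.5% | 91.5% |
| Tier 2, printed | 3.1% | 31% | 67% | 89% | 99% |
| Written rule, ≥6 of 37 | 0.9% | 16.0% | 48.7% | 77.8% | 98.3% |
| One lower, ≥5 of 37 | 3.6% | 31.0% | 67.0% | 88.8% | 99.5% |

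Both printed tables fit limits one DLT below the written rules, within one percentage point in every column. The grade 5 trigger does not explain the Tier 1 gap. With an assumed 0 to 25% of DLTs lethal, the written rule gives 44% to 62% at a true rate of 20%, short of 73%. Both sets of limits are therefore carried forward.

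**Step 2: probability of passing at a true rate of 20%.**
- Tier 1 as written: P(X ≤ 2) = 0.0687 + 0.2062 + 0.2835 = 0.558.
- Tier 1 as tabulated: P(X ≤ 1) = 0.0687 + 0.2062 = 0.275.
- Both rules as written: the sum over x = 0, 1, 2 of P(X₁₂ = x) × P(X₂₅ ≤ 5 − x) = 0.0687 × 0.6167 + 0.2062 × 0.4207 + 0.2835 × 0.2340 = 0.195.
- Both rules as tabulated (at most 1 of 12 and at most 4 of 37): 0.0687 × 0.4207 + 0.2062 × 0.2340 = 0.077.

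Under the written limits the probability of passing both rules is 46% at a true rate of 15% and 1.5% at 30%.

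**Step 3: effect of the grade 5 trigger.** The documents give no share of DLTs that are lethal. If f is that share, the Tier 1 pass probability is the sum over x = 0 to 2 of C(12, x) × [p(1 − f)]^x × (1 − p)^(12 − x). At p = 0.20 it falls from 56% (f = 0) to 52% (f = 5%, assumed) or 48% (f = 10%, assumed). The figures in Step 2 are therefore maxima for the limits they use.

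**Step 4: what a passing count excludes.** The exact (Clopper-Pearson) one-sided 95% upper limit is the 0.95 quantile of Beta(x + 1, n − x).

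| DLTs / patients | Upper limit | Role |
|---|---|---|
| 0/12 | 22.1% | best possible Tier 1 result |
| 1/12 | 33.9% | largest pass, tabulated limit |
| 2/12 | 43.8% | largest pass, written limit |
| 3/37 | 19.6% | largest count that excludes 20% |
| 4/37 | 23.1% | largest pass, tabulated limit |
| 5/37 | 26.3% | largest pass, written limit |

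No Tier 1 result excludes a 20% DLT rate at this confidence level. Over 37 patients a 20% rate is excluded only with 3 or fewer DLTs, which is fewer than either version of the rule allows.

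**The case against.** The strongest reply is that, in Tier 1, safe means no more than safe enough to expand. Section 8.1.1 does say that in one sentence, and the Tier 2 rule then covers all 37 patients. This stands as far as it goes: the 56% describes an interim decision, and the figure for passing both rules is 19.5%. But the other Tier 1 sentence carries no such qualifier, and 8.1.2 repeats it for Tier 2, after which no expansion follows.

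A second reply is that the sentence is not the whole safety evaluation. That also stands. The listed primary safety endpoints are the Tier 2 starting dose level and the identification of DLTs and possibly the maximum tolerated dose. Section 12.6.3 defines a Safe Minimum Dose. Section 12.5 sends toxicity reports to the safety board at the end of each tier. The end-of-trial claim in 12.1.1 is limited to preliminary efficacy and feasibility, on an endpoint that requires responders to be free of DLT. None of these provisions estimates or bounds the DLT rate among all treated patients.

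Four stronger readings are tempting, and the documents do not support them:
- A reader might infer that the plan calls 20% and 30% unacceptable. The tables list them as true rates and label none of them.
- A reader might infer that 30% remains open at the end of the trial. At 5/37 the upper limit of 26.3% excludes it.
- A reader might take 56% as the plan's own figure. The Tier 1 table implies 100% − 73% = 27% considered safe at a true rate of 20%. The 56% printed there is the probability of declaring unsafe at 15%.
- A reader might conclude that the rules, or the tables, are the mistaken part. The documents do not show which was intended.

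**Conclusion.** The point holds as a fault of inference and reporting. Both sections move from an uncrossed boundary to a statement of safety, and nothing else in the plan supplies an estimate or bound for the DLT rate. At a true rate of 20%, the written count limits let therapy pass Tier 1 up to 56% of the time and both tiers up to 19.5% of the time. For the limits that the tables fit, the figures are 27.5% and 7.7%. At one-sided 95% confidence, non-triggering alone fails to exclude 20% in either tier and fails to exclude 30% in Tier 1, whichever set of limits applies.

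These figures assume full evaluability over the 12-week window and one DLT rate across patients. That is a simplification in a trial with intra-patient escalation. The pass probabilities also ignore the grade 5 trigger, which can only lower them. The change is worth making because it is cheap and it limits what may be claimed on a primary objective.

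**What to change.** 1. In 8.1.1 and 8.1.2, replace the conclusion that therapy is considered safe with a statement that the stopping boundary was not crossed. For Tier 1, add that the study may then proceed to Tier 2 if the other criteria are met. For Tier 2, add that no further safety conclusion follows from this alone. Amend the Tier 1 sentence about expansion in the same way.
2. In 12.4.1 or 12.6.1, require the DLT proportion in all treated patients with its exact one-sided 95% upper limit, and confine the safety conclusion to the rate that this limit excludes. Section 12.6.1 is still to be completed, so it is a natural place.
3. Reconcile each written rule with its probability table before any upper limit is quoted beside it, because the values differ (43.8% or 33.9% for Tier 1; 26.3% or 23.1% for both tiers).

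The cost is a few sentences of protocol text and one interval in the report. No patients or visits are added, and the stopping counts are not changed by items 1 and 2. The downside is a less favourable safety statement.
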